6.6.6 Vital Signs

Descriptive statistics for vital signs parameters (i.e., diastolic and systolic BP, resting pulse rate, respiratory rate, temperature) and changes from baseline will be presented by visit and dosing cohort.

6.6.7 Electrocardiograms

ECG findings (categorized as normal; abnormal, not clinically significant; and abnormal, clinically significant) at baseline and unscheduled visit will be summarized.

In addition, the number (percentage) of subjects with at least one postbaseline abnormal ECG result in QTc Fridericia values during the treatment period will be summarized. Clinically abnormal ECG results in Fridericia values will be categorized as follows:

Change from baseline in QTc interval:

- At least one postbaseline increase of >30 ms
- At least one postbaseline increase of >60 ms
- At least one postbaseline value of >450 ms

- At least one postbaseline value of >480 ms
- At least one postbaseline value of >500 ms

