Exclusion Criteria #17 Changed to “Has a history of (non-infectious) pneumonitis that required steroids or current pneumonitis.”	Updated to remain consistent with the latest pembrolizumab protocol template provided by Merck (“Pembrolizumab Text for Eisai PN150 06-Jun-2016	
• Clinical Protocol synopsis• Section 9.3.2
Exclusion Criteria #20 Changed to “Has received a live-virus vaccination within 30 days of planned start of study therapy. Seasonal flu vaccines that do not contain live virus are permitted.”	Updated to remain consistent with the latest pembrolizumab protocol template provided by Merck (“Pembrolizumab Text for Eisai PN150 06-Jun-2016	
• Clinical Protocol synopsis• Section 9.3.2
Added text that tumor assessments are to be performed every 9 weeks \pm 1 week after the start of study treatment (or sooner if there is evidence of progressive disease).	Clarification of text describing timing of tumor assessments if there is evidence of progressive disease.	
• Clinical Protocol synopsis• Section 9.5.1.4.1• Schedule of Procedures/ Assessments
ECG assessments (both before and after eribulin infusion) at Baseline/C1D1 and C1D8 have been included in the safety assessments.	One Screen Visit determination for ECG may be insufficient in order to confirm the safety profile or detect any safety alert (eg, QTc prolongation) of the eribulin plus pembrolizumab combination.	
• Clinical Protocol synopsis• Section 9.5.1.6.6• Schedule of Procedures/ Assessments
Revised definition for the Evaluable Analysis Set	Using the modified evaluable analysis set will more accurately estimate the primary efficacy endpoint (ORR).	
• Clinical Protocol synopsis• Section 9.7.1.2
Updated description of clinical experience with Pembrolizumab	Revised to remain consistent with the latest pembrolizumab protocol template provided by Merck (“Pembrolizumab Text for” Eisai PN150 06-	
• Section 7.1.3.2

Change	Rationale	Affected Protocol Section
	Jun-2016).	
Text revised that describes reasons for discontinuation from the study.	The eCRF does not collect “primary” and “secondary” reasons for discontinuation. Unnecessary to name eCRF form being used to collect study disposition, so such text is deleted.	
Section 9.3.3Section 9.5.5

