9.5.1.6.6 ELECTROCARDIOGRAMS

Electrocardiograms will be obtained as designated in the Schedule of Procedures/Assessments ([Table 8](#)). Complete, standardized, 12-lead ECG recordings that permit all 12 leads to be displayed on a single page with an accompanying lead II rhythm strip below the customary 3×4 lead format are to be used. In addition to a rhythm strip, a minimum of 3 full complexes should be recorded from each lead simultaneously. Subjects must be in the recumbent position for a period of 5 minutes prior to the ECG. Electrocardiograms obtained at C1D1 and C1D8 should be performed just prior to and immediately after receiving the eribulin mesylate infusion.

An ECG abnormality may meet the criteria of an AE as described in this protocol (see [Section 9.5.1.6](#)) and the CRF Completion Guidelines. In these instances, the AE corresponding to the ECG abnormality will be recorded on the Adverse Events CRF.

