- a: End of Treatment assessments for all subjects will be collected within 30 days of the last dose of study drug. Subjects with SAEs and/or ECIs at the time of End of Treatment will be followed for 90 days after the last dose of study drug or, if the subject initiates new anticancer therapy, for 30 days following the last dose of study drug, whichever is earlier. However, treatment-emergent peripheral neuropathy of any grade will be followed until resolution or until another anticancer therapy is started, whichever occurs first. All SAEs should be followed to resolution or, if resolution is unlikely, to stabilization.
- b: Demography information includes date of birth (or age), sex, and race/ethnicity.
- c: TNM staging at the time of diagnosis should be recorded in the eCRF.
- d: A serum (6-mL blood sample will be collected) or urine β -hCG test will be performed at the Screening Visit for premenopausal women and postmenopausal women who have been amenorrheic for less than 12 months. If a negative screening pregnancy test is obtained more than 72 hours before the planned first dose of pembrolizumab and eribulin mesylate, a separate serum or urine sample must be obtained and tested at the Baseline Visit assessment on C1D1.
- e: Pharmacokinetic blood samples will be collected only for eribulin mesylate PK analysis. Time points for PK sample collections are as follows: For all Phase 1b subjects, PK samples will be collected on C1D1 at predose (0 hour), 15, 30 minutes and 1, 2, 4, 8, 24, 48, 72, 96, 120, and 144 hours after the study drug infusion. For Phase 2 subjects, PK samples will be collected, if feasible, on C1D1 (at the end of the infusion, 0.5 to 6 hours and 24 to 120 hours after study drug infusion) and on C1D8 (predose and at the end of the infusion).
- f: Electrocardiogram (ECG) will be performed at Screening, C1D1, C1D8, and at any unscheduled visits as clinically indicated. ECGs obtained at C1D1 and C1D8 should be performed just prior to and immediately after receiving the eribulin mesylate infusion.

- g: Hematology laboratory assessment must be reviewed prior to every eribulin mesylate administration. Cycle 1 Day 1 hematology assessments may be performed within 3 days prior to the scheduled visit. Subsequent hematology assessments may be performed within 24 hours before the scheduled visit.

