9.7.1.8.6 ELECTROCARDIOGRAMS

Electrocardiogram results will be evaluated on an individual basis by subject. Abnormal readings will be identified as those outside (above or below) the reference range. Electrocardiogram findings will be summarized.

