8 DEFINITIONS AND CONVENTIONS FOR DATA HANDLING

Baseline

Baseline is defined as the non-missing value most recently collected before the first dose of any study drug.

In the analyses of ORR, CBR and DCR, subjects without baseline or postbaseline tumor assessment will be considered as non-responders and will be included in the denominator when calculating ORR, CBR and DCR. Non-responders will be excluded in the analysis of DOR.

Study Day 1

Study Day 1 is defined as the day of the first dose of any study drug administrated.

By-visit analysis

All by-visit analyses will be performed using assessment at corresponding scheduled visits recorded in the eCRF (not including unscheduled).

The unscheduled visits will be included in the analyses that involve definition of worst post-baseline assessment.

Definition of BOR by RECIST 1.1

The definition of BOR by RECIST 1.1 will follow Appendix 3 in protocol. In particular,

- Tumor assessments after any new anti-cancer therapy, including the palliative radiotherapy, will be deleted in defining BOR.
- Tumor assessment after PD defined by RECIST 1.1 will be deleted in defining BOR.
- The following BOR responses are defined based on the timepoint-level response
 - Complete Response (CR): A BOR of CR requires two timepoint assessments of CR, with the second at least 4 weeks after the initial CR. An intervening timepoint assessment of PR, SD, or PD prevents confirmation. BOR of CR cannot be preceded by PD.
 - Partial Response (PR): A BOR of PR requires a first assessment of PR and a second assessment of PR (or CR) at least 4 weeks after the initial PR. An intervening timepoint assessment of PD prevents confirmation. BOR of PR cannot be preceded by PD.
 - Stable Disease (SD): A BOR of SD is assessed if the criteria for BOR of CR,or PR-are not met and if, in addition, an assessment of SD (or better) has been documented at least once \geq 8 weeks from the first dose of study treatment.
 - Progressive Disease (PD): A BOR of PD is defined by any timepoint assessment of PD with no prior BOR qualifying as SD, PR, or CR.
 - Not evaluable (NE): A BOR of NE refers to subjects with either no postbaseline tumor assessment(s) or with postbaseline tumor assessment(s) that are not evaluable [i.e., due to insufficient data for assessment of response per applied response criteria RECIST 1.1 or an early SD with duration $<$ 8 weeks].
 - Unknown response (UNK): A BOR of UNK refers to subjects with no baseline tumor assessment

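### The SAP's categorical ECG findings table leaves out the scheduled postbaseline ECGs on Cycle 1 Day 1 and Cycle 1 Day 8

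*SAP*

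**What the plan says.** **Collection.** Table 8, footnote f, of the protocol states: "Electrocardiogram (ECG) will be performed at Screening, C1D1, C1D8, and at any unscheduled visits as clinically indicated". Protocol 9.5.1.6.6 adds the timing: "Electrocardiograms obtained at C1D1 and C1D8 should be performed just prior to and immediately after receiving the eribulin mesylate infusion". The C1D1 and C1D8 recordings came in with Amendment 01. The rationale in the amendment history is: "One Screen Visit determination for ECG may be insufficient in order to confirm the safety profile or detect any safety alert (eg, QTc prolongation").

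**Analysis in the protocol.** Protocol 9.7.1.8.6 has ECG results reviewed subject by subject, with readings outside the reference range identified. It then says: "Electrocardiogram findings will be summarized". It names no visits.

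**Analysis in the SAP.** SAP 6.6.7 contains two ECG analyses.

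- The three-category findings (normal; abnormal, not clinically significant; abnormal, clinically significant) "at baseline and unscheduled visit will be summarized".
- In addition, the number and percentage of "subjects with at least one postbaseline abnormal ECG result in QTc Fridericia values during the treatment period will be summarized". The categories are increases above 30 and 60 ms and values above 450, 480 and 500 ms.

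**Conventions.** SAP Section 8 states: "Baseline is defined as the non-missing value most recently collected before the first dose of any study drug". It also states: "All by-visit analyses will be performed using assessment at corresponding scheduled visits recorded in the eCRF (not including unscheduled"). It admits unscheduled visits to analyses that use the worst postbaseline assessment.

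**The concern.** The scheduled C1D1 and C1D8 recordings are the only on-treatment ECGs that the protocol asks for regardless of the subject's condition. The findings table passes over them and takes its on-treatment content from unscheduled visits, which occur when a clinician has a reason to look. Findings from such a selected set cannot describe how often treated subjects develop an abnormal tracing.

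QTc prolongation is given as an example of the alerts these ECGs might reveal, not as the only one. Changes in rhythm or conduction and ischaemic changes would show in the categorical reading and not in a QTcF count. The protocol's own Table 4 lists myocarditis among the immune-related events attributed to pembrolizumab, so non-QTc findings are relevant to this combination. Safety and tolerability are the primary objective of Phase 1b and a secondary objective of the study (protocol 8.1 and 8.2).

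**Working it through.** The plan gives no figure to reproduce and the point depends on no power or error-rate calculation. The check is to place each scheduled ECG against each planned analysis.

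**Inputs.** ECG times: protocol 9.5.1.6.6 and Table 8, footnote f. Dosing order on Day 1 (pembrolizumab, then eribulin immediately): protocol 9.4.1. Baseline rule: SAP Section 8. Analyses: SAP 6.6.7 and 6.6.3.

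| ECG | Findings table | QTcF outlier count |
|---|---|---|
| Screening | Yes, if it is the last value before any study drug | Reference value only |
| C1D1 pre-eribulin, taken before pembrolizumab | Yes, as baseline | Reference value only |
| C1D1 pre-eribulin, taken after pembrolizumab | No | Yes |
| C1D1 post-eribulin | No | Yes |
| C1D8 pre-eribulin | No | Yes |
| C1D8 post-eribulin | No | Yes |
| Unscheduled, on treatment | Yes | Yes |

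**Step 1: what is missing.** Three scheduled postbaseline recordings per subject are outside the findings table: one on C1D1 and two on C1D8, 1 + 2 = 3. A fourth is outside if the C1D1 pre-eribulin tracing was taken after pembrolizumab. That can happen because the tracing is timed to eribulin, which is given second, while baseline must precede any study drug.

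**Step 2: consistency with the protocol.** Protocol 9.7.1.8.6 has no visit restriction; SAP 6.6.7 has one and gives no reason. Protocol 9.7.5 requires departures from the protocol's analysis plan to be documented in the SAP.

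**Step 3: consistency within the SAP.** Section 8 bases by-visit summaries on scheduled visits and brings in unscheduled ones for worst-value analyses. Section 6.6.7 does the reverse for findings. Related data are handled more fully: laboratory values by visit with a shift to worst grade (6.6.5), vital signs by visit (6.6.6), and ECOG status by visit with a shift to worst value (6.6.8).

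**Step 4: whether another analysis covers the gap.** The QTcF count covers every postbaseline tracing, but only for QTc. Protocol 9.5.1.6.6 sends an ECG abnormality to the Adverse Events CRF when it meets the AE criteria, and SAP 6.6.3 tabulates treatment-emergent events by system organ class and preferred term. Neither covers a categorical, non-QTc abnormality at a scheduled time that was not reported as an adverse event. SAP 6.7 plans no other analysis.

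**The case against.** The strongest reply is that the signal named when these ECGs were added is analysed. The QTcF paragraph has no visit restriction, so the C1D1 and C1D8 tracings are in it. Abnormalities important enough to be adverse events appear in the TEAE tables, and each subject's ECG is to be evaluated individually under protocol 9.7.1.8.6. That section does not call for a by-visit table. The table shells are in a separate document (SAP Section 11) and may contain more. This is one descriptive table in a study that the SAP calls exploratory.

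Most of this stands, and it sets the limit of the point. It does not remove it: SAP 6.6.7 states which visits enter the findings table, and the scheduled postbaseline ones are not among them. Shells that nobody reading the SAP can see do not correct an explicit sentence in it.

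Three stronger readings are tempting, and the documents do not support them.

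- A reader might infer that the scheduled ECGs go unanalysed, or that QTc prolongation would be missed. The QTcF count rules that out.
- A reader might multiply 170 planned subjects by 3 tracings and report 510 omitted recordings. Amendment 01 is dated 03 August 2016, while enrolment was estimated to begin in August 2015. Subjects who finished Cycle 1 before the amendment had no such ECGs scheduled, and some may not have reached C1D8. The documents give neither number.
- A reader might say that the on-treatment abnormality rate has a biased denominator. SAP 6.6.7 defines neither a rate nor a denominator for this table. What can be said is that its only on-treatment readings are clinically triggered.

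**Conclusion.** The point holds in a limited form. As written, SAP 6.6.7 leaves the scheduled postbaseline ECGs out of the categorical findings table, is narrower than protocol 9.7.1.8.6, and departs from the convention in SAP Section 8. The information lost is the categorical, non-QTc reading at scheduled times for abnormalities not reported as adverse events.

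The size is up to three tracings per subject under the schedule as amended, or four where the C1D1 pre-eribulin ECG followed pembrolizumab. The number of subjects affected cannot be derived from the documents. The unclear status of that pre-eribulin ECG also reaches the QTcF analysis, because it decides which tracing is the reference for the change from baseline.

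The conclusion assumes that the wording of SAP 6.6.7 governs and that the three-category reading was recorded for the scheduled tracings. No efficacy result or primary analysis depends on it. It is worth correcting because it is a stated rule that gives a poorer safety summary than the collected data allow.

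**What to change.** Amend SAP 6.6.7 so that the three-category ECG findings are summarised:

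- at baseline;
- at C1D1 after eribulin, C1D8 before eribulin and C1D8 after eribulin, with the denominator at each time being the subjects who have an ECG at that time;
- as a shift from baseline to the worst postbaseline category, including unscheduled ECGs.

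Add one sentence stating that the C1D1 pre-eribulin ECG counts as baseline only if it was taken before the first dose of any study drug, and otherwise as postbaseline. Apply the same rule to the QTcF change from baseline. The time-specific denominators accommodate subjects treated before Amendment 01 and those who did not reach C1D8.

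The cost is one descriptive table from data already collected. No extra ECG is needed, and the QTcF categories and the primary analysis stay as they are.

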6.6.8 Other Safety Analyses

ECOG performance status will be summarized descriptively by visit and by shift from baseline to worst postbaseline.

6.7 Other Analyses

No other analysis is planned.

6.8 Exploratory Analyses

Exploratory analyses may be conducted as appropriate. Any exploratory analyses that are performed will be appropriately titled/labeled as exploratory and will be clearly distinguished from planned analyses when results are reported in the Clinical Study Report.

7 INTERIM ANALYSES

The Interim Analysis Set includes all subjects treated at RP2D level who have either completed two post-baseline tumor assessments or discontinued early. The planned interim analysis will be performed when there are 38 such subjects. If the number of subjects in the Interim Analysis Data Set is not exactly 38 at the time of the interim analysis, the Bayesian stopping boundaries will be adjusted based upon the current information ([Appendix 13.1](#))

Interim decisions can be made on the basis of the expected response rate at the end of the study, which compromises the current information with the future sample size via predictive probability approach. The Bayesian design can continuously update the predictive probability of the study outcome, such that early termination of a study is possible for either superiority or futility. The pre-specified Bayesian stopping boundaries are included in [Appendix 13.1](#).

The study statistician will work with the clinical study managers and data managers to define the datasets for the interim analysis. The study statistician will assess the impact of any issues such as unsolved data queries, missing data or data entry delays on the interim results.

If the protocol needs to be revised after the study starts, the sponsor will determine how the revision impacts the study and how the revision should be implemented. The details of the revision will be documented and described in the clinical study report.

8 DEFINITIONS AND CONVENTIONS FOR DATA HANDLING

Baseline

Baseline is defined as the non-missing value most recently collected before the first dose of any study drug.

In the analyses of ORR, CBR and DCR, subjects without baseline or postbaseline tumor assessment will be considered as non-responders and will be included in the denominator when calculating ORR, CBR and DCR. Non-responders will be excluded in the analysis of DOR.

Study Day 1

Study Day 1 is defined as the day of the first dose of any study drug administrated.

By-visit analysis

All by-visit analyses will be performed using assessment at corresponding scheduled visits recorded in the eCRF (not including unscheduled).

The unscheduled visits will be included in the analyses that involve definition of worst post-baseline assessment.

Definition of BOR by RECIST 1.1

The definition of BOR by RECIST 1.1 will follow Appendix 3 in protocol. In particular,

- Tumor assessments after any new anti-cancer therapy, including the palliative radiotherapy, will be deleted in defining BOR.
- Tumor assessment after PD defined by RECIST 1.1 will be deleted in defining BOR.
- The following BOR responses are defined based on the timepoint-level response
 - Complete Response (CR): A BOR of CR requires two timepoint assessments of CR, with the second at least 4 weeks after the initial CR. An intervening timepoint assessment of PR, SD, or PD prevents confirmation. BOR of CR cannot be preceded by PD.
 - Partial Response (PR): A BOR of PR requires a first assessment of PR and a second assessment of PR (or CR) at least 4 weeks after the initial PR. An intervening timepoint assessment of PD prevents confirmation. BOR of PR cannot be preceded by PD.
 - Stable Disease (SD): A BOR of SD is assessed if the criteria for BOR of CR,or PR-are not met and if, in addition, an assessment of SD (or better) has been documented at least once \geq 8 weeks from the first dose of study treatment.
 - Progressive Disease (PD): A BOR of PD is defined by any timepoint assessment of PD with no prior BOR qualifying as SD, PR, or CR.
 - Not evaluable (NE): A BOR of NE refers to subjects with either no postbaseline tumor assessment(s) or with postbaseline tumor assessment(s) that are not evaluable [i.e., due to insufficient data for assessment of response per applied response criteria RECIST 1.1 or an early SD with duration $<$ 8 weeks].
 - Unknown response (UNK): A BOR of UNK refers to subjects with no baseline tumor assessment

Definition of BOR by irRECIST

- Investigator Review

Subjects who experience PD defined by RECIST1.1 will have a confirmation scan at least 4 weeks apart to confirm PD (irPD). Subjects may continue receiving study treatment while waiting for confirmation of irPD if they are clinically stable. If a subject discontinued study treatment without confirmation of irPD, the subject will be counted as irPD.

Tumor assessments after any new anti-cancer therapy, including the palliative radiotherapy, will be deleted in defining BOR. The overall time point tumor response data collected via both the CRF of the irRECIST and the CRF of the RECIST 1.1 will be used. Simply add prefix 'ir' to CR/PR/SD/PD/NE from RECIST 1.1 and follow the definition of BOR per RECIST 1.1 to define BOR per irRECIST (irCR/irPR/irSD/irPD/irNE). Table 2 describes the scenarios of PD by RECIST 1.1 followed by different confirmation scans.

Table 2. BOR by irRECIST for Scenarios with PD (defined by RECIST 1.1) Followed by Subsequent Scans

Timepoint 1 Overall Response	Timepoint 2 (\geq 4 weeks since Timepoint 1) Overall Response	BOR by irRECIST
PD	CR ^a	If subject has been followed for \geq 4 weeks and CR is confirmed, BOR is irCR. If CR not confirmed, then follow same rule as BOR by definition of RECIST 1.1.
PD	PR ^a	If subject has been followed for \geq 4 weeks and PR is confirmed, BOR is irPR. If PR not confirmed, then follow same rule as BOR by definition of RECIST 1.1.
PD	SD ^b	irSD
PD	PD ^c	irPD
PD	NE	irPD
PD		irPD, if no confirmation scan.

^a The subject should be followed for \geq 4 weeks to confirm the CR/PR.

^b The subject is on the study treatment and followed for further tumor assessments.

^c PD is confirmed. The subjects should be discontinued from the study treatment, and no further tumor response assessments will be performed.

Other exploratory endpoints using irRECIST: ORR, PFS, DOR, CBR and DCR will be derived similarly as those using RECIST1.1; but the derivation will be based on irCR, irPR, irSD and irNE instead of CR, PR, SD and NE.

- Independent Imaging Review

BOR by irRECIST for IIR data will follow the same principle as above except tumor assessments by mRECIST 1.1(modified RECIST 1.1) criteria for the time points up to PD are used.

Censoring rule for OS

Subjects who are lost to follow-up or withdrawal from study will be censored at the last date the subject was known to be alive, and subjects who remained alive will be censored at the time of data cutoff.

Censoring rule for PFS by RECIST 1.1

The PFS derivation rules in this SAP follow the sensitivity of analyses described in Food and Drug Administration (FDA) “[Guidance for Industry Clinical Trial Endpoints for the Approval of Cancer Drugs and Biologics \(2007\)](#)”.

Definition of Progression Date: Progression date is assigned to the first time at which radiological progression can be declared.

For progression based on a new lesion, the progression date is the date of the initial detection of the new lesion, if there were multiple new lesions detected, then the earliest date of initial detection will be used.

Table 3 shows the primary censoring rules for the derivation of PFS based upon investigator's tumor assessment.

Censoring rule for irPFS by irRECIST

Definition of progression date by irRECIST (i.e., irPD):

- For the subjects who experience PD by RECIST 1.1 and then confirmed by irPD ($>$ or <28 days) or not confirmed due to any reasons, the first documented PD date by RECIST 1.1 is the date of irPD.
- For the subjects who experience PD by RECIST1.1 and then followed by irCR/irPR/irSD, the first documented progression date is the date of first irPD defined by irRECIST.
- If the subject had new lesion earlier than overall timepoint response of PD in irRECIST, the date of new lesion is not counted as irPD date. (this is different from PD by RECIST 1.1 for which, as soon as subject developed new lesions, subject is considered as PD and PD date is the date of new lesion).

Censoring rule will be same as RECIST1.1 except that for the second rule in [Table 3](#).

“Date of first radiologic PD assessment” means the irPD Date determined as above.

Duration of Response

Duration of Response (DOR) – defined as the time from the date that a confirmed objective response is first documented to the date of PD or death due to any cause for those subjects with a confirmed PR or CR. For subjects who did not experience PD or death by the end of data cut off, the date of last adequate radiologic assessment before missing tumor assessments or new anti-cancer therapy will be used as censoring date.

BOR, PFS and DOR will be defined separately for IIR data and for investigator reviewed data following the same rules.

Table 3. Censoring Rules for Analysis of Progression-Free Survival

No.	Situation	Date of Progression or Censoring	Outcome
1	No baseline or post-baseline tumor assessments	Date of the first dose	Censored
2	Progression documented between scheduled visits	Date of first radiologic PD assessment	Progressed
3	No progression at the time of data cut-off	Date of last adequate radiologic assessment prior to or on date of data cut-off	Censored
4	New anticancer treatment started	Date of last adequate radiologic assessment prior to or on date of new anticancer treatment	Censored
5	Death before first PD assessment	Date of death	Progressed
6	Death between adequate assessment visits*	Date of death	Progressed
7	Death or progression after two or more missed visit**	Date of last adequate radiologic assessment before missed tumor assessments	Censored

CR = complete response, PD = progressive disease, PR = partial response, SD = stable disease,

* Adequate tumor assessment is a radiologic assessment of CR, PR, SD, non-CR/non-PD or PD as determined by investigators.

New anticancer treatment includes palliative radiotherapy. Any tumor assessments after new anticancer treatment started will be removed in the definition of PFS.

** More than two missed visits is defined if the duration between the last tumor assessment (including NE) and death or PD is longer than 126 days (18 weeks) or 168 days (e.g. 24 weeks) for subjects on the every 9 or 12 week scanning schedule in this study:

The priority of the censoring rules is as follows:

1. If the subject had PD or death, the following sequence will be applied:

- If a subject did not have baseline tumor assessment (No. 1), the subject will be censored on date of the first dose. However, if the subject did not have baseline tumor assessment and died within 126 days (18 weeks) after the first dose and did not receive new anticancer treatment, the date of death will be the PFS event date (not censored).
- If a subject had new anticancer treatment before PD or death (No. 4), the subject will be censored on the date of the last adequate tumor assessment prior to or on the date of new anticancer treatment.
- If a subject missed two assessments before PD or death (No. 7), the subject will be censored on the date of the last adequate tumor assessment before PD or death. Note that if a subject is censored by both this criterion and the anticancer treatment criteria, the earliest

censoring date will be used.

- Otherwise, if a subject had an event (No. 2, No. 5, or No. 6), the earliest event date will be used.

2. If a subject did not have PD or death, the censoring date will be the earliest censoring date if the subject met multiple censoring criteria (No. 1, No. 3, No. 4, No. 7).

Rules for missing dates:

In case of dates missing in adverse event and concomitant medication collection following rules will be followed.

- **Adverse Events**

Adverse Events with incomplete start dates will be considered treatment emergent if:

- a. Day and month are missing and the year is equal to or after the year of the first dose date;
- b. Day is missing, and the year is after the year of the first dose;
- c. Day is missing and the year is equal to the year of the first dose date and the month is equal to or after the month of the first dose date;
- d. Year is missing; or
- e. Complete date is missing.

- **Concomitant Medications**

Medications will be considered concomitant if:

- a. Day and month are missing and the year is equal to or after the year of the first dose date;
- b. Day is missing, and the year is after the year of the first dose;
- c. Day is missing and the year is equal to the year of the first dose date and the month is equal to or after the month of the first dose date; or
- d. Year is missing; or complete date is missing.

Pharmacokinetics/Pharmacodynamic Data Handling

- **Lower Limit of Quantification of Eribulin Plasma Concentration**

The Lower Limit of Quantification (LLOQ) of eribulin plasma concentration is 0.200 ng/mL.

- **Below Limit of Quantification Handling for Calculation of Pharmacokinetic Parameters**

While calculating PK parameters in Phoenix/WinNonlin, BLQ values will be handled according to the [NCA-MNL](#).

- **BLQ Handling for Developing Concentration-Time Profiles**

When developing individual concentration-time profiles, BLQ values will be handled according to the [NCA-MNL](#).

- **Handling of Anomalous Concentration Values**

The handling of anomalous concentration values will follow the guidance in the [NCA-MNL](#).

- **General Rules for Presentation of Drug Concentrations and PK Parameters**

When presenting individual/raw (raw, hereafter) values and summary statistics, the following rule will be applied: for drug concentrations and concentration-dependent pharmacokinetic parameters, all summary statistics (mean, median, geometric mean, SD, and CV) will have 3 significant digits. For t_{max} and t_{lag} , raw values and median have fixed 2 decimal places.

Table 4. General Rules for Presentation of Drug Concentrations and PK Parameters

Typical variable	Standard Unit (depends on compound)	N	Digit rule	Raw Minimum Maximum	Mean Median	SD	Geometric Mean	CV (%)
E2027 concentration	ng/mL	X	Significant digits	3	3	3	-	-
C_{max} , C_{min}	ng/mL	X	Significant digits	3	3	3	3	3
t_{max} , t_{lag}^a	h	X	Fixed decimal places	2	2	-	-	-
λ_z	1/h	X	Significant digits	3	3	3	3	3
$t_{1/2}$	h	X	Significant digits	3	3	3	3	3
AUC	ng·h/mL	X	Significant digits	3	3	3	3	3
%AUC _{ex}	%	X	Significant digits	3	3	3	3	3
CL	L/h	X	Significant digits	3	3	3	3	3
V_d	L	X	Significant	3	3	3	3	3

Typical variable	Standard Unit (depends on compound)	N	Digit rule	Raw Minimum Maximum	Mean Median	SD	Geometric Mean	CV (%)
			digits					
MRT	h	X	Significant digits	3	3	3	3	3

a: Mean, SD, geometric mean and CV will not be calculated for t_{\max} and t_{lag} .

CV(%) = $\text{sqrt}(\text{exp}[\text{SD}^2 \text{ of log transformed data}]-1) \times 100$

